1.0 TRIAL SUMMARY

Abbreviated Title	Phase 1/1b Trial of MK-1966 in Combination with SD-101 in Subjects with Advanced Malignancies
Sponsor Product Identifiers	MK-1966, SD-101 N/A
Trial Phase	Phase I/Ib
Clinical Indication	Part A- Treatment of subjects with B-cell lymphoma, melanoma, squamous cell cancer of head and neck, breast cancer with dermal metastasis Part B- Treatment of subjects with melanoma Part C- Treatment of subjects with squamous cell cancer of head and neck
Trial Type	Interventional
Type of control	None
Route of administration	MK-1966 given intravenously and SD-101 given intratumorally
Trial Blinding	Unblinded Open-label
Treatment Groups	Part A: Dose escalation of MK-1966 in combination with a fixed dose of SD-101 in subjects with B-cell lymphoma, melanoma, squamous cell cancer of head and neck, breast cancer with dermal metastasis. Part B: Confirmation/Expansion Cohort of maximum tolerated dose/maximum administered dose MTD (maximum tolerated dose) /MAD (maximum administered dose) of MK-1966 with fixed dose SD-101 in melanoma. Part C: Confirmation/Expansion Cohort of MTD/MAD of MK-1966 with fixed dose SD-101 in squamous cell cancer of head and neck.
Number of trial subjects	Approximately 64 subjects will be enrolled.
Estimated duration of trial	The Sponsor estimates that the trial will require approximately 1.8 years from the time the first subject signs the informed consent until the last subject's last study-related phone call or visit.

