Duration of Participation	Each subject will participate in the trial from the time the subject signs the Informed Consent Form (ICF) through the final contact. After a screening phase of up to 28 days, eligible subjects will be enrolled in Part A treatment with MK-1966 and SD-101 and will continue for up to 8 cycles (approximately 24 weeks) of treatment. Treatment in Parts B and C will be with the MTD or MAD of MK-1966 determined in Part A. Subjects in Parts A, B and C may receive up to 8 cycles (approximately 24 weeks) of treatment or continue treatment until disease progression, unacceptable adverse event(s), intercurrent illness that prevents further administration of treatment, Investigator's decision to withdraw the subject, subject withdraws consent, pregnancy of the subject, noncompliance with trial treatment or procedure requirements, or administrative reasons requiring cessation of treatment. After the end of treatment (EOT), each subject will be followed for 30 days. Serious adverse events (SAEs) will be collected for 30 days after EOT.
Randomization Ratio	N/A

A list of abbreviations used in this document can be found in Section 12.6.

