3.3 Exploratory Objectives

- 1) **Objective:** To evaluate the objective response rate (ORR), disease control rate (DCR), best overall response (BOR), best target lesion response, time to confirmed response, duration of response (DOR), progression-free survival (PFS) and overall survival (OS) of subjects with advanced tumors treated with the combination of MK-1966 with SD-101 by Cheson criteria (for B Cell lymphoma) or irRECIST (for melanoma, squamous cell cancer of head and neck, breast cancer with dermal metastasis) as assessed by investigator review.
- 2) **Objective:** To investigate the relationship between candidate efficacy biomarkers and anti-tumor activity of MK-1966 in combination with SD-101.
 - a. Tumor microenvironment features including infiltrating lymphocytes (CD3+ total T cells and CD8+ T cells) and plasmacytoid dendritic cells.
 - b. IFN α and its associated gene expression profiles in pre and post treatment peripheral blood and tumor biopsies
 - c. To correlate the clinical response to pre-treatment gene sequence expression profiles.
- 3) **Objective:** To investigate the relationship between anti-tumor activity of MK-1966 in combination with SD-101 with potential patient selection biomarkers PD-L1 and TLR9 in pre-treatment tumor biopsies.
- 4) **Objective:** To evaluate the effect of MK-1966 in combination with SD-101 on immune activation biomarkers including IL-10, IFN- γ , IL-12p70, IL-13, IL-1 β , IL-2, IL-4, IL-6, IL-8 TNF- α and IFN- α 2a.
- 5) **Objective:** To evaluate development of circulating anti-MK-1966.
- 6) **Objective:** To explore the relationship between genomic variation and response to the treatment(s) administered. Variation across the human genome (germline and tumor) will be analyzed for association with clinical data collected in this study.
- 7) **Objective:** To evaluate the longitudinal change of tumor size.

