4.2.3.5 Cheson Criteria for Lymphomas

Response to treatment will be evaluated by the investigator at 12 weeks and 24 weeks after the first study injection. Response to treatment will continue to be assessed every 12 weeks that a subject remains in the trial.

Response of lesions will be assessed by CT or CT/PET and bone marrow biopsy using the Cheson criteria for lymphomas [24]. Response will be assessed on the basis of clinical, radiologic, and pathologic (ie, bone marrow) criteria:

1. At a minimum, thoracic, abdominal, and pelvic CT scans will be performed even if those areas were not initially involved because of the unpredictable pattern of recurrence in NHL. CT/PET may be used if they are the standard tools for assessing disease status at a participating institution.
2. Unilateral bone marrow biopsy and aspirates will be performed at Screening if not previously performed or if performed more than 90 days previously with negative results. The bone marrow biopsy will be performed to confirm a complete response (CR) if the subject was initially positive or if it is clinically indicated by new abnormalities in the peripheral blood counts or blood smear.

Response of lesions will be recorded on the CRF based on the definitions in [Table 3](#) as appropriate. Suspected relapse or disease progression must be confirmed by physical exam, laboratory assessments, repeat bone marrow biopsy [24] and CT scan. If confirmed,

progressive disease should be reported to the sponsor within 7 days. Subjects with suspected relapse or disease progression should continue to follow study procedures until they need another therapy. If a subject requires another therapy, date of treatment and type of treatment will be recorded and they will then be removed from the trial.

Tumor progression is defined as $\geq 50\%$ increase from nadir in the sum of the products of the greatest diameters (SPD), as defined in the Cheson response criteria for NHL [24]. The response criteria should be recorded in the database. However, if the subject is evaluated by CT/PET scan then tumor response criteria should be evaluated using updated Cheson criteria [25] which includes CT and PET scans.

Table 3 Response Criteria for Non-Hodgkin's Lymphoma

Response Category	Physical Examination	Lymph Nodes	Lymph Node Masses	Bone Marrow
Complete Response	Normal	Normal	Normal	Normal
Complete Response/ Unconfirmed	Normal	Normal	Normal	Indeterminate
	Normal	Normal	$\geq 75\%$ decrease	Normal or indeterminate

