5.5.2 Prohibited Concomitant Medications

Subjects are prohibited from receiving the following therapies during the Screening, and Treatment Phases of this trial:

- Immunotherapy not specified in this protocol.
- Antineoplastic systemic chemotherapy or biological therapy. Investigational agents not specified in this protocol.
- Radiation therapy; radiotherapy for symptom management is allowed.
- Live vaccines within 30 days prior to the first dose of trial treatment and while participating in the trial. Examples of live vaccines include, but are not limited to, the following: measles, mumps, rubella, chicken pox, yellow fever, rabies, BCG, and typhoid vaccine. Seasonal influenza vaccines for injection are generally killed virus vaccines and are allowed. However, intranasal influenza vaccines (e.g. Flu - Mist®) are live attenuated vaccines, and are not allowed.

Glucocorticoids for any purpose other than to modulate symptoms from an adverse event. Glucocorticoids must be below 10 mg daily to restart SD-101 and/or MK-1966 dosing. Chronic systemic replacement doses of steroids are allowed. Inhaled steroids for management of asthma are allowed.

Subjects who, in the assessment by the investigator, require the use of any of the aforementioned treatments for clinical management should be removed from the trial. Subjects may receive other medications that the investigator deems to be medically necessary.

There are no prohibited therapies during the Follow-up visits.

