5.9 Subject Withdrawal/Discontinuation Criteria

Subjects may withdraw consent at any time for any reason or be dropped from the trial at the discretion of the investigator should any untoward effect occur. In addition, a subject may be withdrawn by the investigator or the Sponsor if enrollment into the trial is inappropriate, the trial plan is violated, or for administrative and/or other safety reasons. Specific details regarding discontinuation or withdrawal procedures; including specific details regarding withdrawal from Future Biomedical Research, are provided in Section 7.1.4 – Other Procedures.

In this trial, a subject may discontinue from treatment but continue to participate in the regularly scheduled activities, as long as the subject does not withdraw consent. Once a subject has discontinued treatment, even though he/she continues to be monitored in the trial, he/she may be allowed to begin treatment again if deemed medically appropriate.

A subject must be discontinued from the trial for any of the following reasons:

- The subject or legal representative (such as a parent or legal guardian) withdraws consent.

A subject must be discontinued from treatment (but may continue to be monitored in the trial) for any of the following reasons:

- Confirmed disease progression per response assessment criteria (See Section 4.2.3)
- Noncompliance with trial treatment or procedure requirements
- Investigator's decision to withdraw the subject
- Clinical progression
- Subject has a confirmed pregnancy test
- Unacceptable adverse events
- Intercurrent illness that prevents further administration of treatment
- Administrative reasons
- Lost to follow-up

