- g. MK-1966 Pharmacokinetics (PK) samples will be collected more frequently in Cycles 1-3. On Days 1, 22 and 43 -collect predose, at the end of infusion and 2h after the start of the infusion (+10 minutes). On Day1 of Cycles 4-8 collect PK samples predose. Also collect PK Samples on Days 2, 3, 8, 15, 29, 36, 50, 57, at the treatment discontinuation, and Safety Follow-up visit (30 days post end of treatment).
- h. Blood samples for IL-10 Pharmacodynamics (PD) will be drawn at Screening and at times that match PK sampling in footnote “i” above.
- i. Unilateral bone marrow biopsy and aspirate will be performed at Screening if not previously performed or if performed more than 90 days previously with negative results. The bone marrow biopsy will be performed to confirm a CR if the subject was initially positive or if it is clinically indicated by new abnormalities in the peripheral blood counts or blood smear (section 4.2.3.5)
- j. When SD-101 and MK-1966 are scheduled on the same day, SD-101 will be administered first. MK-1966 will be administered at least 30 minutes after the SD-101 injection.
- k. These samples may be performed up to 72 hours prior to dosing. However, in Cycle 1 on Day 1, samples are to be drawn prior to dosing and should be used as the subject's baseline (not screening) values.
- l. Include HCV, RNA (qualitative) or Hepatitis C antibody, HBsAg, and HIV type 1 and type 2 (e.g., HIV-1/-2 antibody screening test and evaluation of HIV viral load as needed).
- m. Patients who discontinue from treatment or have completed post treatment follow up should be contacted every three months to monitor overall survival (for up to 2 years from last dose of study drug or until the sites are notified by the Sponsor that the survival follow up is no longer required).
- n. The Day 9 visit must be 24 hours (+/- 4 hours) after the Day 8 visit.
- o. Sample(s) and/or procedures will be collected prior to dosing and when applicable as outlined in the Procedures Manual.
- p. Record all AEs occurring from signing of informed consent until 30 days after the last dose of MK-1966 and SD-101. Report all SAEs occurring up to 30 days after the last dose of treatment
- q. Dosing with MK-1966 and/or SD-101 will occur within the timeframes outlined in section 5.2.5. and/or the Procedures Manual.
- r. After the SD-101 is injected, the injection site should be observed every 15 minutes for at least 90 minutes.

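### Clauses that take subjects out of the trial at next therapy, a 1.8-year duration and a lock 24 weeks after last enrolment do not fit the plan's own survival follow-up of up to 2 years

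*Combined protocol and SAP*

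**What the plan says.** Overall survival (OS) is part of an exploratory objective (3.3): "progression-free survival (PFS) and overall survival (OS) of subjects with advanced tumors". The flow chart (6.0, footnote m) supplies the follow-up: "Patients who discontinue from treatment or have completed post treatment follow up should be contacted every three months to monitor overall survival". This runs for at most 2 years from last dose, or until the sponsor tells sites that it is no longer needed.

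On who leaves the trial, the text divides:

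- Section 5.5.2: those who, during screening or treatment, "require the use of any of the aforementioned treatments for clinical management should be removed from the trial". The section adds that nothing is prohibited at the follow-up visits.
- Section 4.2.3.5 (lymphoma, Part A only): once another therapy is required, "date of treatment and type of treatment will be recorded and they will then be removed from the trial".
- Section 5.9: its list of mandatory trial exits contains only withdrawal of consent. Confirmed and clinical progression stand under a different lead-in: "A subject must be discontinued from treatment (but may continue to be monitored in the trial) for any of the following reasons".

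On timing, the trial summary (1.0) states: "After the end of treatment (EOT), each subject will be followed for 30 days". Section 7.1.5.2 repeats this. Neither mentions survival contact. The summary estimates 1.8 years from first consent to the last subject's "last study-related phone call or visit". Section 8.2 locks the database about 24 weeks after the last subject enrols. Section 8.6.3.5 derives 1.8 years from accrual plus 24 weeks, in both planning scenarios.

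**The concern.** A subject on treatment who comes to need another anticancer therapy falls under 5.5.2 (or 4.2.3.5) and under footnote m together, and these give opposite instructions. If the site closes the subject out, later deaths go unrecorded. Entry requires disease that has progressed on earlier therapy (5.1.2), so need for another therapy is likely to track worsening disease. Loss at that moment would then be related to prognosis, and OS estimates that treat it as non-informative censoring would tend to be too favourable.

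The second problem does not depend on the first. Even if every subject stays in follow-up, the stated duration and lock date leave no time for what footnote m asks of sites. Many survival calls would then produce data after the only lock the plan describes.

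**Working it through.** **Trial exit, side by side**

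| Section | Trigger | Effect on trial participation |
|---|---|---|
| 5.5.2 | prohibited therapy needed in screening or treatment phase | leaves the trial |
| 4.2.3.5 | Part A lymphoma, another therapy needed | therapy recorded, leaves the trial |
| 5.9 | confirmed or clinical progression | stops treatment, may stay in the trial |
| 5.9 | consent withdrawn | leaves the trial |
| 7.1.4.1 | stops treatment early | encouraged to stay for remaining visits |
| 7.1.4.1 | leaves the trial | final-visit activities done at that point |
| 6.0, footnote m | off treatment | survival contact every three months |

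The first two rows cannot both stand with the last one for a subject whose need for next therapy arises on treatment. No section says which prevails.

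**Calendar.** Years = weeks × 7 / 365.25. Inputs: one subject enrolled per week; 64 weeks of accrual (Scenario 2) or 52 (Scenario 1); 24 weeks of treatment (8.6.3.5); 28 days of screening and 30 days of safety follow-up (1.0). The last MK-1966 dose comes 7 × 3 = 21 weeks after the first (5.2, Table 5). Footnote m adds at most 104 weeks.

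*Reproducing the stated 1.8 years*

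- Scenario 2, accrual plus treatment: 64 + 24 = 88 weeks = 1.69 years.
- Plus the 30-day visit: 92.3 weeks = 1.77 years.
- Plus screening: 96.3 weeks = 1.85 years.
- Scenario 1: 52 + 24 = 76 weeks = 1.46 years; with screening and the 30-day visit, 84.3 weeks = 1.62 years.

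So 1.8 years fits Scenario 2 with about 30 days after treatment and no survival follow-up. It does not fit Scenario 1, for which 8.6.3.5 gives the same figure.

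*With footnote m at full length*

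- 64 subjects: 64 + 21 + 104 = 189 weeks = 3.6 years.
- 52 subjects: 52 + 21 + 104 = 177 weeks = 3.4 years.
- 64 subjects, last one stopping after a single dose: 64 + 104 = 168 weeks = 3.2 years.

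*What exists at lock (Scenario 2).* Lock falls at week 64 + 24 = 88. A subject enrolled in week i has 88 − i weeks of potential follow-up: 24 for the last, 87 for the first, median 55.5. A completer's full schedule is 21 + 104 = 125 weeks, so on average 55.5 / 125 = 44% of it has elapsed. Since 87 < 104, nobody can have 2 years after last dose, not even a subject who stopped after one dose. In Scenario 1 the range is 24 to 75 weeks, median 49.5.

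*Illustration of the information lost to an early cut.* The documents give no survival rate, so this assumes exponential OS with no other censoring in Scenario 2. Deaths observed = average of 1 − exp(−ln 2 × follow-up / median).

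| Assumed median OS | Observed by lock | Observed by 2 years after last dose (completers) |
|---|---|---|
| 6 months | 74% | 96% |
| 12 months | 51% | 81% |
| 18 months | 38% | 67% |
| 24 months | 30% | 57% |

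This cut is administrative: it costs events and does not by itself bias the estimate. Only the loss at next therapy raises a question of bias.

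**The case against.** The strongest reply is that the plan can be read to keep subjects in follow-up. The ban in 5.5.2 covers screening and treatment only. Under 5.9 a progressing subject stops treatment first, and may then start new therapy with nothing prohibited. Sections 7.1.1.5.2 and 7.1.5.2.1 foresee new anticancer therapy and ask only that the safety visit come before it. Section 5.5 itself speaks of stopping trial therapy. The lymphoma clause reaches part of Part A (at most 24 of 64 subjects in Scenario 2, across four tumour types). Two years is a ceiling that the sponsor may lower. OS is exploratory, and its methods are left to a supplemental SAP.

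Most of this stands, and it limits the point. A reader might infer that OS will be censored at progression, or that a definite overestimate of survival can be calculated. The documents do not support either:

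- No section gives an OS censoring rule, and the trigger in both clauses is need for another therapy, not progression. The nearest text, in 7.1.2.6.3.1, says a subject should not leave the trial before progression is confirmed. It does not order an exit afterwards, and 5.9 treats confirmed progression as a reason to stop treatment.
- Any figure for the bias needs a progression rate, a death rate before progression and the share of subjects removed. None is given.

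Nor does the trial necessarily close at 1.8 years. That is an estimate, and 5.11 ends the trial at the last call or visit, which can include survival calls.

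What the reply leaves standing is the literal wording of 5.5.2 and 4.2.3.5 for subjects still on treatment, and a stated duration and lock that allow for none of the survival follow-up beyond that date. A supplemental SAP cannot recover deaths that sites never recorded.

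**Conclusion.** The plan contradicts itself in two places.

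- **Participation.** Sections 5.5.2 and 4.2.3.5 conflict with 5.9 and footnote m on whether a subject who needs another therapy stays in the trial. The consequence is a risk of selective loss of survival data under a literal reading. It is not a planned censoring rule, and its size is unknown. Calling it informative rests on the judgement that need for next therapy tracks prognosis here.
- **Timing.** The 1.8 years is accrual, treatment and about 30 days. The survival schedule can need up to 3.6 years (3.4 for 52 subjects). At lock, follow-up from enrolment is 24 to 87 weeks. This is arithmetic from the plan's own figures, assuming one enrolment per week, a last subject who completes 8 cycles and no early end to survival contact by the sponsor.

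The 1.8 years printed for Scenario 1 is also wrong by its own sum (1.46 years). OS is exploratory with no event target stated, so this should be corrected but does not touch the primary DLT/MTD objective.

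**What to change.** 1. Reconcile 5.5.2 and 4.2.3.5 with 5.9 and footnote m, on trial participation only: subjects who need another therapy stay in survival follow-up unless they withdraw consent. No treatment-stopping rule need change.
2. Section 5.2.3.1 speaks in one place of discontinuing the agent and in another of discontinuing from the study when further toxicity or a further dose reduction arises. These should be reconciled. Which treatment rule applies is for the clinical team. This clause is driven by toxicity and is not part of the argument about next therapy.
3. In 1.0 and 7.1.5.2, label the 30 days as safety follow-up and add the survival contact.
4. Restate the duration for 64 subjects as about 1.7 to 1.8 years to end of treatment and safety follow-up, and up to about 3.6 years to the last survival call. Alternatively, shorten footnote m to match the duration intended. Correct the Scenario 1 figure.
5. State an OS censoring rule and a survival data cut later than the lock in 8.2, and analyse OS from that cut.

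The cost is protocol wording, a longer stated duration (unless footnote m is shortened) and one more data transfer. The calls themselves are already in the flow chart.

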5.6 Treatment Precaution

IFN- α has been shown to inhibit cytochrome P450 (CYP) enzyme 1A2 (Brennan 2012). Since SD 101 induces IFN- α , SD 101 may inhibit metabolism of drugs by CYP 1A2. CYP 1A2 substrates with narrow therapeutic ranges should be used with caution. The following drugs should be used with caution through 7 days after each subsequent dose of SD-101: caffeine, theophylline, warfarin, tricyclic antidepressants, clozapine, fluvoxamine, ciprofloxacin, propranolol, and verapamil.

5.7 Rescue Medications & Supportive Care

5.7.1 Supportive Care Guidelines

Subjects should receive appropriate supportive care measures as deemed necessary by the treating investigator. Suggested supportive care measures for the management of adverse events with potential immunologic etiology are outlined below. Where appropriate, these guidelines include the use of oral or intravenous treatment with corticosteroids as well as additional anti-inflammatory agents if symptoms do not improve with administration of corticosteroids. Note that several courses of steroid tapering may be necessary as symptoms may worsen when the steroid dose is decreased. For each disorder, attempts should be made to rule out other causes such as metastatic disease or bacterial or viral infection, which might require additional supportive care. The treatment guidelines are intended to be applied when the investigator determines the events to be related to MK-1966 or SD-101.

It may be necessary to perform conditional procedures such as bronchoscopy, endoscopy, or skin photography as part of evaluation of the event.

- **Diarrhea/Colitis:**

Subjects should be carefully monitored for signs and symptoms of enterocolitis (such as diarrhea, abdominal pain, blood or mucus in stool, with or without fever) and of bowel perforation (such as peritoneal signs and ileus).

- All subjects who experience diarrhea/colitis should be advised to drink liberal quantities of clear fluids. If sufficient oral fluid intake is not feasible, fluid and electrolytes should be substituted via IV infusion. For Grade 2 or higher diarrhea, consider GI consultation and endoscopy to confirm or rule out colitis.
- For **Grade 2 diarrhea/colitis** that persists greater than 3 days, administer oral corticosteroids.
- For **Grade 3 or 4 diarrhea/colitis** that persists > 1 week, treat with intravenous steroids followed by high dose oral steroids.
- When symptoms improve to Grade 1 or less, steroid taper should be started and continued over no less than 4 weeks.

- **Hyperthyroidism or Hypothyroidism:**

Thyroid disorders can occur at any time during treatment. Monitor patients for changes in thyroid function (at the start of treatment, periodically during treatment, and as indicated based on clinical evaluation) and for clinical signs and symptoms of thyroid disorders.

- **Grade 2** hyperthyroidism events (and **Grade 3-4** hypothyroidism):
 - In hyperthyroidism, non-selective beta-blockers (e.g. propranolol) are suggested as initial therapy.
 - In hypothyroidism, thyroid hormone replacement therapy, with levothyroxine or liothyroinine, is indicated per standard of care.
- **Grade 3-4** hyperthyroidism
 - Treat with an initial dose of IV corticosteroid followed by oral corticosteroids. When symptoms improve to Grade 1 or less, steroid taper should be started and continued over no less than 4 weeks. Replacement of appropriate hormones may be required as the steroid dose is tapered.

- **Hepatic:**

- For **Grade 2** events, monitor liver function tests more frequently until returned to baseline values (consider weekly).
 - Treat with IV or oral corticosteroids
- For **Grade 3-4** events, treat with intravenous corticosteroids for 24 to 48 hours.
- When symptoms improve to Grade 1 or less, a steroid taper should be started and continued over no less than 4 weeks.

- **Hypophysitis:**

- For **Grade 2** events, treat with corticosteroids. When symptoms improve to Grade 1 or less, steroid taper should be started and continued over no less than 4 weeks. Replacement of appropriate hormones may be required as the steroid dose is tapered.
- For **Grade 3-4** events, treat with an initial dose of IV corticosteroids followed by oral corticosteroids. When symptoms improve to Grade 1 or less, steroid taper should be started and continued over no less than 4 weeks. Replacement of appropriate hormones may be required as the steroid dose is tapered.

- **Management of Infusion Reactions:** Signs and symptoms usually develop during or shortly after drug infusion and generally resolve completely within 24 hours of completion of infusion.

[Table 8](#) below shows treatment guidelines for subjects who experience an infusion reaction associated with administration of MK-1966 or SD-101.

Table 8 Infusion Reaction Treatment Guidelines

NCI CTCAE Grade	Treatment	Premedication at Subsequent Dosing
Grade 1 Mild reaction; infusion interruption not indicated; intervention not indicated	Increase monitoring of vital signs as medically indicated until the subject is deemed medically stable in the opinion of the investigator.	None
Grade 2 Requires infusion interruption but responds promptly to symptomatic treatment (e.g., antihistamines, NSAIDS, narcotics, IV fluids); prophylactic medications indicated for <=24 hrs	
Stop Infusion.
 
Additional appropriate medical therapy may include but is not limited to:
 
 IV fluids Antihistamines NSAIDS Acetaminophen Narcotics 
Increase monitoring of vital signs as medically indicated until the subject is deemed medically stable in the opinion of the investigator.
 
If symptoms resolve within one hour of stopping drug infusion, the infusion may be restarted at 50% of the original infusion rate (e.g. from 100 mL/hr to 50 mL/hr). Otherwise dosing will be held until symptoms resolve and the subject should be premedicated for the next scheduled dose.
 
Subjects who develop Grade 2 toxicity despite adequate premedication should be permanently discontinued from further trial treatment administration.
	
Subject may be premedicated 1.5h (\pm 30-minutes) prior to infusion of MK-1966 with:
 
 Diphenhydramine 50 mg po (or equivalent dose of antihistamine). Acetaminophen 500-1000 mg po (or equivalent dose of analgesic).
Grades 3 or 4 Grade 3: Prolonged (i.e., not rapidly responsive to symptomatic medication and/or brief interruption of infusion); recurrence of symptoms following initial improvement; hospitalization indicated for other clinical sequelae (e.g., renal impairment, pulmonary infiltrates) Grade 4: Life-threatening; pressor or ventilatory support indicated	
Stop Infusion.
 
Additional appropriate medical therapy may include but is not limited to:
 
 IV fluids Antihistamines NSAIDS Acetaminophen Narcotics Oxygen Pressors Corticosteroids Epinephrine 
Increase monitoring of vital signs as medically indicated until the subject is deemed medically stable in the opinion of the investigator.
 
Hospitalization may be indicated.
 
Subject is permanently discontinued from further trial treatment administration.
	No subsequent dosing
Appropriate resuscitation equipment should be available at the bedside and a physician readily available during the period of drug administration.		
For Further information, please refer to the Common Terminology Criteria for Adverse Events v4.0 (CTCAE) at http://ctep.cancer.gov		

- Management of Injection Site Reaction(s):
 - Subjects should receive full supportive care to treat injection site reactions.. Injection-site reactions are expected to spontaneously subside. Local reactions

are to be treated at the discretion of the treating physician. The site is not to be injected if local pain, tenderness, or swelling persists from a previous injection or other cause; the injection may be postponed until the symptoms have resolved. The injection may be skipped, following agreement with the Medical Monitor.

- **Pneumonitis:** For **Grade 2 events**, treat with systemic corticosteroids. When symptoms improve to Grade 1 or less, steroid taper should be started and continued over no less than 4 weeks.
 - For **Grade 3-4 events**, immediately treat with intravenous steroids. Administer additional anti-inflammatory measures, as needed.
 - Add prophylactic antibiotics for opportunistic infections in the case of prolonged steroid administration.
- **Renal Failure or Nephritis:**
 - For Grade 2 events, treat with corticosteroids
 - For Grade 3-4 events, treat with systemic corticosteroids
 - When symptoms improve to Grade 1 or less, steroid taper should be started and continued over no less than 4 weeks.
- **Type 1 Diabetes Mellitus** (if new onset, including diabetic ketoacidosis) or \geq Grade 3 hyperglycemia, if associated with ketosis (ketonuria) or metabolic acidosis (diabetic ketoacidosis)
 - Insulin replacement therapy is recommended for Type 1 diabetes mellitus and for Grade 3-4 hyperglycemia associated with metabolic acidosis or ketonuria.
 - Evaluate patients with serum glucose and a metabolic panel, urine ketones, glycosylated hemoglobin, and C-peptide.

